**Table 14.2.1**  
**Summary of Mini-Mental State Examination**  
**(ITT Population)**

Parameter	Visit	Statistics	Actual (N=xxx)	Change from baseline (N=xxx)
Orientation	Baseline	n	xx	
		Mean $\pm$ SD	xx.x $\pm$ xx.xx	
		Q 1	xx.x	
		Median	xx.x	
		Q 3	xx.x	
		(Min, Max)	(xx.x , xx.x)	
	Visit 2	n	xx	xx
		Mean $\pm$ SD	xx.x $\pm$ xx.xx	xx.x $\pm$ xx.xx
		Q 1	xx.x	xx.x
		Median	xx.x	xx.x
		Q 3	xx.x	xx.x
		(Min, Max)	(xx.x , xx.x)	(xx.x , xx.x)
	EOS	n	xx	xx
		Mean $\pm$ SD	xx.x $\pm$ xx.xx	xx.x $\pm$ xx.xx
		Q 1	xx.x	xx.x
		Median	xx.x	xx.x
		Q 3	xx.x	xx.x
		(Min, Max)	(xx.x , xx.x)	(xx.x , xx.x)
	Registration	n	xx	
		Mean $\pm$ SD	xx.x $\pm$ xx.xx	
		Q 1	xx.x	

**Catalogue of Tables, Listings and Figures**  
**Sponsor: Novartis**

**Study Number: [REDACTED] Version: Final 1.0 Date: 01 Dec 2022**

Parameter	Visit	Statistics	Actual (N=xxx)	Change from baseline (N=xxx)
		Median	xx.x	
		Q 3	xx.x	
		(Min, Max)	(xx.x , xx.x)	
	Visit 2	n	xx	xx
		Mean ± SD	xx.x ± xx.xx	xx.x ± xx.xx
		Q 1	xx.x	xx.x
		Median	xx.x	xx.x
		Q 3	xx.x	xx.x
		(Min, Max)	(xx.x , xx.x)	(xx.x , xx.x)
	EOS	n	xx	xx
		Mean ± SD	xx.x ± xx.xx	xx.x ± xx.xx
		Q 1	xx.x	xx.x
		Median	xx.x	xx.x
		Q 3	xx.x	xx.x
		(Min, Max)	(xx.x , xx.x)	(xx.x , xx.x)
.....	.....	.....	.....	.....
Total	Baseline	n	xx	
		Mean ± SD	xx.x ± xx.xx	
		Q 1	xx.x	
		Median	xx.x	
		Q 3	xx.x	
		(Min, Max)	(xx.x , xx.x)	
	Visit 2	n	xx	xx
		Mean ± SD	xx.x ± xx.xx	xx.x ± xx.xx

**Catalogue of Tables, Listings and Figures**  
**Sponsor: Novartis**

**Study Number:** [REDACTED] **Version: Final 1.0 Date: 01 Dec 2022**

Parameter	Visit	Statistics	Actual (N=xxx)	Change from baseline (N=xxx)
		Q 1	xx.x	xx.x
		Median	xx.x	xx.x
		Q 3	xx.x	xx.x
		(Min, Max)	(xx.x , xx.x)	(xx.x , xx.x)
EOS		n	xx	xx
		Mean ± SD	xx.x ± xx.xx	xx.x ± xx.xx
		Q 1	xx.x	xx.x
		Median	xx.x	xx.x
		Q 3	xx.x	xx.x
		(Min, Max)	(xx.x , xx.x)	(xx.x , xx.x)

N: Total number of patient's in the ITT population

n: Total number of patients in a given category

Analysis Dataset: XXXX

Source Listing: Listing xx.x.x

**Programming note:**

**This table will consists of five sections (orientation, registration, attention-calculation, recall, and language & Praxis) and Total**

Catalogue of Tables, Listings and Figures  
Sponsor: Novartis

Study Number: [REDACTED] Version: Final 1.0 Date: 01 Dec 2022

**Table 14.2.2: Summary of ADCS ADL-Severe Dementia Version**

Novartis  
[REDACTED]

ddmmmyyyy hh:mm  
Page x of y

Table 14.2.2  
Summary of ADCS ADL-Severe Dementia Version  
(ITT Population)

ADCS ADL	(N=xx)	n (%)
Eating,,		xx (xx.x)
Walking		xx (xx.x)
Bowel and Bladder		xx (xx.x)
Bathing,,		xx (xx.x)
Grooming,,		xx (xx.x)
---		---

N: Total number of patient's in the ITT population

Analysis Dataset: XXXX

Source Listing: Listing xx.x.x

**Catalogue of Tables, Listings and Figures**  
**Sponsor: Novartis**

**Study Number:** [REDACTED] **Version: Final 1.0 Date: 01 Dec 2022**

**Table 14.2.2.1: Summary and change from baseline of ADCS ADL-Severe Dementia Version total score**

Novartis

*ddmmmyyyy hh:mm  
Page x of y*

Table 14.2.2.1

Summary and change from baseline of ADCS ADL-Severe Dementia Version total score  
(ITT Population)

Visit	Statistics	Actual (N=xxx)	Change from baseline (N=xxx)
Baseline	n Mean $\pm$ SD Q 1 Median Q 3 (Min, Max)	xx xx.x $\pm$ xx.xx xx.x xx.x xx.x (xx.x , xx.x)	
Visit 2	n Mean $\pm$ SD Q 1 Median Q 3 (Min, Max)	xx xx.x $\pm$ xx.xx xx.x xx.x xx.x (xx.x , xx.x)	xx xx.x $\pm$ xx.xx xx.x xx.x xx.x (xx.x , xx.x)
EOS	n Mean $\pm$ SD Q 1 Median Q 3 (Min, Max)	xx xx.x $\pm$ xx.xx xx.x xx.x xx.x (xx.x , xx.x)	xx xx.x $\pm$ xx.xx xx.x xx.x xx.x (xx.x , xx.x)
EOS	n Mean $\pm$ SD Q 1 Median	xx xx.x $\pm$ xx.xx xx.x xx.x	xx xx.x $\pm$ xx.xx xx.x xx.x

**Catalogue of Tables, Listings and Figures**  
**Sponsor: Novartis**

**Study Number: [REDACTED] Version: Final 1.0 Date: 01 Dec 2022**

Visit	Statistics	Actual (N=xxx)	Change from baseline (N=xxx)
	Q 3 (Min, Max)	xx.x (xx.x , xx.x)	xx.x (xx.x , xx.x)

N: Total number of patient's in the ITT population

Analysis Dataset: XXXX

Source Listing: Listing xx.x.x

**Catalogue of Tables, Listings and Figures**  
**Sponsor: Novartis**

**Study Number: [REDACTED] Version: Final 1.0 Date: 01 Dec 2022**

**Table 14.2.3: Summary of Responses on the Caregiver Medication Questionnaire**

Novartis  
[REDACTED]

ddmmmyyyy hh:mm  
Page x of y

Table 14.2.3  
Summary of Responses on the Caregiver Medication Questionnaire Mean scores  
(ITT Population)

Visit	Parameter	Category	Statistics	Total (N=xx) n (%)
Visit2	During the past 1 week	A patch ever skipped	Never	xx (xx.xx)
			1 day	xx (xx.xx)
			2 days	xx (xx.xx)
			3 days	xx (xx.xx)
			4 or more days	xx (xx.xx)
		The patch taken later than intended	Never	xx (xx.xx)
			1 day	xx (xx.xx)
			2 days	xx (xx.xx)
			3 days	xx (xx.xx)
			4 or more days	xx (xx.xx)
Extent of agreement		I was concerned that my patient missed taking his / her patch medication	Always	
			Most of the time	

**Catalogue of Tables, Listings and Figures**  
**Sponsor: Novartis**

**Study Number:** [REDACTED] **Version: Final 1.0 Date: 01 Dec 2022**

Visit	Parameter	Category	Statistics	Total (N=xx)
				n (%)
		Sometimes		
		Rarely		
		Never		
	I found it difficult to remember to administer the patch medication	Always		
		Most of the time		
		Sometimes		
		Rarely		
		Never		
Overall compliance		n	xx	
		Mean ± SD	xx.x ± xx.x	
satisfied or dissatisfied		Q1	xx.x	
		Median	xx.x	
		Q3	xx.x	
		(Min, Max)	(xx.x , xx.x)	
		n	xx	
		Mean ± SD	xx.x ± xx.x	
		Q1	xx.x	
		Median	xx.x	
		Q3	xx.x	
		(Min, Max)	(xx.x , xx.x)	

**Catalogue of Tables, Listings and Figures**  
**Sponsor: Novartis**

**Study Number:** [REDACTED] **Version: Final 1.0 Date: 01 Dec 2022**

Visit	Parameter	Category	Statistics	Total (N=xx)	n (%)
Visit3	---	---	--	--	--

N: Total number of patient's in the ITT population

Analysis Dataset: XXXX

Source Listing: Listing xx.x.x

**Programming note:**

**This table will consist of mean scores of Visit-2 (8 + 2 weeks) and Visit-3 (16+ 2 weeks)**

**Catalogue of Tables, Listings and Figures**  
**Sponsor: Novartis**

**Study Number: [REDACTED] Version: Final 1.0 Date: 01 Dec 2022**

**Table 14.3.1: Overall Summary of Adverse Events**

Novartis  
[REDACTED]

*ddmmmyyyy hh:mm  
Page x of y*

Table 14.3.1  
Overall Summary of Adverse Events  
(Safety Population)

	Total (N=xxx) n (%) E
Adverse Events	xx (xx.x) xx
Treatment Emergent Adverse Events	xx (xx.x) xx
Serious Adverse Events	xx (xx.x) xx
Adverse Event related to study drug	xx (xx.x) xx
Adverse Events Leading to Study Medication Discontinuation	xx (xx.x) xx
Adverse Events Leading to death	xx (xx.x) xx
AE's by maximum severity	
Mild	xx (xx.x) xx
Moderate	xx (xx.x) xx
Severe	xx (xx.x) xx

N = Total number of patients in the safety population

n: number of patients with atleast one AE in the specified field. E: Number of Events

This table includes only the treatment emergent adverse events

Percentages are based on the total number of patient's under Safety population

Adverse Events will be coded using the Medical Dictionary of Regulatory Activities (MedDRA version 20.1)

Analysis Dataset: XXXX

Source Listing: Listing xx.x.x

**Catalogue of Tables, Listings and Figures**  
**Sponsor: Novartis**

**Study Number: [REDACTED] Version: Final 1.0 Date: 01 Dec 2022**

**Table 14.3.2: Summary of Patient's with Adverse Events Classified by System Organ Class, Preferred Term During the Study**

Novartis

ddmmmyyyy hh:mm  
Page x of y

Table 14.3.2

Summary of Patient's with Treatment Emergent Adverse Events Classified by System Organ Class, Preferred Term During the Study  
(Safety Population)

System Organ Class Preferred Term	Total (N=xxx) n (%) E
Number of patients with at least one AE	xx (xx.x) xx
SOC1	xx (xx.x) xx
PT 1	xx (xx.x) xx
....	Xx (xx.x) xx
SOC2	xx (xx.x) xx
PT 1	xx (xx.x) xx
PT 2	xx (xx.x) xx
....	....

N = Total number of patients in the safety population

n: number of patients with atleast one AE in the specified field . E: Number of Events

Patients are counted only once within each Preferred Term and System Organ Class

Percentages are based on the total number of patient's under Safety population

Adverse Events will be coded using the Medical Dictionary of Regulatory Activities (MedDRA version 20.1)

Analysis Dataset: XXXX

Source Listing: Listing xx.x.x

Programming Note:

Note 1: System organ class and preferred term are ordered alphabetically.

Note 2: Patients are counted only once within each Preferred Term and System Organ Class

**Table 14.3.3: Summary of Patients with Adverse Events Classified by System Organ Class, Preferred Term and Severity**

Novartis

ddmmmyyyy hh:mm  
Page x of y

Table 14.3.3

Summary of Patients with Treatment Emergent Adverse Events Classified by System Organ Class, Preferred Term and Severity  
(Safety Population)

System Organ Class Preferred Term	Severity	Total (N=xxx) n (%) E
Number of patients with at least one AE	Mild	xx (xx.x) xx
	Moderate	xx (xx.x) xx
	Severe	xx (xx.x) xx
SOC 1	Mild	xx (xx.x) xx
	Moderate	xx (xx.x) xx
	Severe	xx (xx.x) xx
PT 1	Mild	xx (xx.x) xx
	Moderate	xx (xx.x) xx
	Severe	xx (xx.x) xx
	.....	.....
	.....	.....

N = Total number of patients in the safety population

n: number of patients with at least one AE in the specified field. E: Number of Events

Percentages are based on the total number of patient's under Safety population

Adverse Events will be coded using the Medical Dictionary of Regulatory Activities (MedDRA version 20.1)

Analysis Dataset: XXXX

Source Listing: Listing xx.x.x

Programming Note:

Note 1: System organ class and preferred term are ordered alphabetically.

Note 2: Patients are counted only once within each Preferred Term and System Organ Class

**Catalogue of Tables, Listings and Figures**  
**Sponsor: Novartis**

**Study Number:** [REDACTED] **Version: Final 1.0 Date: 01 Dec 2022**

Table 14.3.4: Summary of Patients with Treatment Emergent Adverse Events Classified by System Organ Class, Preferred Term and Relation to study drug

(Safety Population)

*<Refer to table 14.3.3 for shell format>*

Programming Note:

Note 1: System organ class and preferred term are ordered alphabetically.

Note 2: Patients are counted only once within each Preferred Term and System Organ Class

Table 14.3.5: Summary of Patients with Treatment Emergent Adverse Events Classified by System Organ Class, Preferred Term and Action Taken

(Safety Population)

*<Refer to table 14.3.3 for shell format>*

Programming Note:

Note 1: System organ class and preferred term are ordered alphabetically.

Note 2: Patients are counted only once within each Preferred Term and System Organ Class

Table 14.3.6: Summary of Patients with Treatment Emergent Adverse Events Classified by System Organ Class, Preferred Term and Outcome

(Safety Population)

*<Refer to table 14.3.3 for shell format>*

Programming Note:

Note 1: System organ class and preferred term are ordered alphabetically.

Note 2: Patients are counted only once within each Preferred Term and System Organ Class

**Catalogue of Tables, Listings and Figures**  
**Sponsor: Novartis**

**Study Number:** [REDACTED] **Version: Final 1.0 Date: 01 Dec 2022**

Table 14.3.7: Number and Percentage of Patients with Treatment Emergent Serious Adverse Events Classified by System Organ Class and Preferred Term

(Safety Population)

*<Refer to table 14.3.2 for shell format>*

**Programming Note:**

Note 1: System organ class and preferred term are ordered alphabetically.

Note 2: Patients are counted only once within each Preferred Term and System Organ Class

**Catalogue of Tables, Listings and Figures**  
**Sponsor: Novartis**

**Study Number: EA-CT-18-001**

**Version: Final 1.0 Date: 01 Dec 2022**

**Table 14.3.8: Summary of Skin tolerability during 16 weeks treatment period**

Novartis

*ddmmmyyyy hh:mm  
Page x of y*

Table 14.3.8  
Summary of Skin tolerability during 16 weeks treatment period  
(Safety Population)

Visit	Parameter	Category	Total (N=xx) n (%)
Visit 2	Score to capture comments relating to patch adhesion	0 1 2 3 4	xx (xx.x) xx (xx.x) xx (xx.x) xx (xx.x) xx (xx.x)
	Has patch skin reaction occurred?	Yes No	xx (xx.x) xx (xx.x)
	Score to assess skin irritation (Dermal response)	0 1 2 3 4 5	xx (xx.x) xx (xx.x) xx (xx.x) xx (xx.x) xx (xx.x) xx (xx.x)
	Score to assess skin irritation (Other effects)	Yes No	xx (xx.x) xx (xx.x)
	Other effects	O P	xx (xx.x) xx (xx.x)

**Catalogue of Tables, Listings and Figures**  
**Sponsor: Novartis**

**Study Number:** [REDACTED] **Version: Final 1.0 Date: 01 Dec 2022**

V	xx (xx.x)
B	xx (xx.x)
Pu	xx (xx.x)
H	xx (xx.x)
W	xx (xx.x)
S	xx (xx.x)
A	xx (xx.x)

Visit 3 .... .... ....

---

N: Total number of patient's in the safety population

Analysis Dataset: XXXX

Source Listing: Listing xx.x.x

**Catalogue of Tables, Listings and Figures**  
**Sponsor: Novartis**

**Study Number: [REDACTED] Version: Final 1.0 Date: 01 Dec 2022**

**Table 14.3.9: Summary of proportion of patients with UTI during 16 weeks treatment period**

Novartis  
[REDACTED]

*ddmmmyyyy hh:mm*  
*Page x of y*

Table 14.3.9

Summary of proportion of patients with UTI during 16 weeks treatment period  
(Safety Population)

	Total (N=xx)	n (%)
Summary of patients with UTI		xx (xx.x)

N: Total number of patient's in the safety population

Analysis Dataset: XXXX

Source Listing: Listing xx.x.x

**Catalogue of Tables, Listings and Figures**  
**Sponsor: Novartis**

**Study Number: [REDACTED] Version: Final 1.0 Date: 01 Dec 2022**

**Table 14.3.10: Summary and Change from Baseline of Lab parameters by Visit and Treatment**

Novartis  
[REDACTED]

ddmmmyyyy hh:mm  
Page x of y

Table 14.3.10  
Summary and Change from Baseline of Lab parameters by Visit and Treatment  
(Safety Population)

Lab Category	Parameters	Visit	Statistics*		Actual	Change from baseline
			n	xx		
Chemical	Protein	Baseline	Mean ± SD	xx.x ± xx.xx	xx	xx
			Q 1	xx.x		
			Median	xx.x		
			Q 3	xx.x		
			(Min, Max)	(xx.x , xx.x)		
		Visit 2	Mean ± SD	xx.x ± xx.xx	xx	xx
			Q 1	xx.x		
			Median	xx.x		
			Q 3	xx.x		
			(Min, Max)	(xx.x , xx.x)		

.....  
N = Total number of patients in the safety population

Change from baseline = (Day X – baseline)

Analysis Dataset: XXXX

Source Listing: Listing xx.x.x

Programming note:

This table will consist of Physical (pH, Specific Gravity, Colour and Others), Chemical (Protein, Glucose, Ketones, Others) and Microscopy (Pus, RBC, Epithelial Cell, WBC and Others)

**Catalogue of Tables, Listings and Figures**  
**Sponsor: Novartis**

**Study Number: [REDACTED] Version: Final 1.0 Date: 01 Dec 2022**

**Table 14.3.11: Summary of Overall Interpretation of Laboratory Parameters by Visit and Treatment**

Novartis  
[REDACTED]

ddmmmyyyy hh:mm  
Page x of y

Table 14.3.11  
Summary of Overall Interpretation of Laboratory Parameters by Visit and Treatment  
(Safety Population)

Lab Category	Lab Test	Visit	Categories	(N=xx)	
Chemical	Protein	Baseline	Normal	xx (xx.x)	
			Abnormal-NCS	xx (xx.x)	
			Abnormal-CS	xx (xx.x)	
	Visit 2	Visit 2	Normal	xx (xx.x)	
			Abnormal-NCS	xx (xx.x)	
			Abnormal-CS	xx (xx.x)	
...		...	...	...	
...		...	...	...	

N = Total number of patients in the safety population

n: Total number of patient's in a given category

Percentages are based on the total number of patient's under safety population

Analysis Dataset: XXXX

Source Listing: Listing xx.x.x

Programming note:

This table will consist of Chemical (Protein, Glucose, Ketones and Others) and Microscopy (Pus RBC, Epithelial Cell WBC and Others) and Physical (pH, Specific Gravity, Colour and Others)

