5.5.6 Laboratory evaluations

5.5.6.1 Urinalysis

Complete urine examination will be done at baseline, visit 2 and end of study visit.

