8.7 Sample size calculation

Incidence of adverse event data of ACTION study (74.60%) for Rivastigmine patch per day over a 24-week study period in patients with severe AD.

Sample size is determined based on a precession approach considering normal approximation. A sample of 93 subjects will be able to estimate the incidence rate with an maximum error of

10% of the true population proportion with 90% of the cases. We assumed, the true population proportion is 0.746 (what is observed in US44)

Similarly, a sample of 41 subjects will be able to estimate the incidence rate with an maximum error of 10% of the true population proportion with 85% of the cases and sample of 23 subjects of the true population proportion with 80% of the cases.

Considering drop out of 10% and true population proportion with 90%, 102 patients shall be enrolled.

9 Ethical considerations

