## 8 General Statistical Considerations

### 8.1 Descriptive Statistics

The following descriptive statistics will be calculated for continuous data and for ordered categorical data (ordinal data):

Summary statistics are displayed with the following digits:

Description	Characteristic	Number of decimal places
Count	n	0
Count corresponding to the number of patients for a group	N	0
Mean	Mean	As in source + 1
Standard Deviation	SD	Mean+1
Minimum	Min	As in source
Median	Median	As in source + 1
Maximum	Max	As in source
1st Quartile / 3rd Quartile	Q1/Q3	As in source + 1
Percentage relative to N #	%	1

	Statistical Analysis Plan Sponsor: Novartis
Study Number: [REDACTED]	Version: Final 1.0 Date: 01 Dec 2022

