## 8.2 Analysis Population

Two population will be considered for the analysis: The intend to treat (ITT) population and safety population. Analysis for all efficacy endpoints using the ITT population will be the primary approach for analysis. For safety endpoints, safety population will be used for analysis.

Analysis Population	Definition
Screened Population	All the subjects who screened in the study will be considered
Intend to treat Population	The intend to treat (ITT) set will include all patients having signed the Informed Consent, who have at least one post baseline assessment.
Safety population	The safety set will include all patients who provide Informed Consent to collect information and who were treated with at least one patch of rivastigmine 27 mg- 15 cm  transdermal patch during this study. Of note, the statement that a patient had no AE also constitutes a safety assessment

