#### Safety

No imputation will be done on missing safety data, unless for partially incomplete dates for remote events such as AE, concomitant medication etc.

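### By-visit percentages for urine, vital signs and physical examination (and, by implication, skin and adhesion) are divided by the whole safety population, so missing assessments dilute every category

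*SAP*

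**What the plan says.** **Stated denominator.** SAP Tables 14.3.11, 14.3.13 and 14.3.14 show Normal, Abnormal-NCS and Abnormal-CS by visit. Each defines N as the safety population and carries the footnote "Percentages are based on the total number of patient's under safety population".

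**Implied denominator.** Table 14.3.8 (skin irritation and patch adhesion) has no percentage footnote. It has only "N: Total number of patient's in the safety population". SAP 8.1 lists "Percentage relative to N" and describes N as "Count corresponding to the number of patients for a group".

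**Who is in N.** SAP 8.2 admits to the safety set consenting patients "who were treated with at least one patch of rivastigmine". No post-baseline assessment is required.

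**Missing data.** SAP 8.5.1 applies LOCF to missing week-16 values, but its Safety subsection says "No imputation will be done on missing safety data", with an exception for partial dates. None of the four shells has a row for patients not assessed or prints the number assessed at a visit.

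**Visits.** For urine, Protocol 5.5.6.1 says: "Complete urine examination will be done at baseline, visit 2 and end of study visit". Vital signs and physical examination follow the same three visits. Skin irritation and adhesion are scored only at Visit 2 and EOS (Protocol section 5 and SAP 7.1.1, schedules of assessments).

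**The concern.** A by-visit table is read as the share of patients with a finding at that visit. Here the divisor is everyone who ever wore a patch, including those who left before the visit and those who attended without that assessment. They can enter no numerator, so every printed percentage falls as attendance falls.

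Two things are at stake. First, post-baseline rates are lower than the rates among patients who were examined. The Protocol (section 1.2) names application-site reactions and UTI as the most frequent events in the earlier study, and says that application-site reaction and urine will be assessed here for that reason. The study has a single arm, so no comparator shares the dilution. Protocol 8.5.2 also foresees 95% confidence intervals for proportions where appropriate, and those would inherit the denominator.

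Second, missingness normally grows over time. For urine, vital signs and physical examination, drop-out alone can then produce an apparent fall from baseline to EOS. For skin and adhesion, which have no baseline score, the fall can only run from Visit 2 to EOS.

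**Working it through.** **Inputs**

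- Evaluable and enrolled numbers: 93 and 102, with 10% drop-out (Protocol 8.7, SAP 8.6). The Protocol's words are: "Considering drop out of 10% and true population proportion with 90%, 102 patients shall be enrolled".
- Assumed adverse event incidence 0.746, relative error 10%, 90% confidence (same sections).
- The documents give no by-visit missing fraction. The 10% planning figure is the only one they contain; 5%, 20% and 30% below are assumptions.
- N = 102 assumes that every enrolled patient receives at least one patch.

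**1. Reproduce the plan's own figure**

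n = z² p(1 − p) / (0.10 p)², with z = 1.645 and p = 0.746, gives 92.12, rounded up to 93. Then 93 × 1.1 = 102.3, the stated 102. The plan thus expects about 10% of patients to be lost: 102 × 0.90 = 91.8, or 92 assessed.

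**2. Effect of the denominator**

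Let x be the patients in a category, A those assessed at the visit, and N the safety set.

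- Printed percentage = x/N.
- Percentage among assessed = x/A.
- Printed = (percentage among assessed) × A/N.

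The factor A/N is the same for Normal, Abnormal-NCS and Abnormal-CS, so the three printed percentages sum to A/N.

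**3. Numbers, N = 102**

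| Missing | A | A/N (= sum of categories) | 20% prints as | 30% prints as |
|---|---|---|---|---|
| 5% (assumed) | 97 | 0.951 | 19.0% | 28.5% |
| 10% (planned) | 92 | 0.902 | 18.0% | 27.1% |
| 20% (assumed) | 82 | 0.804 | 16.1% | 24.1% |
| 30% (assumed) | 71 | 0.696 | 13.9% | 20.9% |

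In whole patients, 18 abnormal at a visit with 92 assessed print as 18/102 = 17.6%, against 18/92 = 19.6% among those assessed.

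**4. Apparent trend**

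Suppose the urine abnormality rate among assessed patients is 20% at every visit, with nobody missing at baseline, 5% missing at Visit 2 and 10% missing at EOS. The table prints 20.0%, 19.0% and 18.0%. The decline comes entirely from the divisor.

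**5. Examinations done only if indicated**

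Protocol 5.5.1 makes rectal, external genital, breast and pelvic examinations conditional on history or symptoms, while SAP 9.7.2 lists them with the rest. If Table 14.3.14 reports them over the full N, A/N could be far below any value in the table above. The documents give no figure for it.

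**The case against.** **The rate can be recovered.** Each cell prints a count, and in Tables 14.3.11, 14.3.13 and 14.3.14 the three categories are exhaustive. Their sum is therefore the number assessed, and a reader can rebuild the rate. Tables 14.3.10 and 14.3.12 show n by visit, Table 14.1.4 shows attendance, and the footnote discloses the divisor. This stands, and it limits the harm. The printed percentages are still diluted, and they are what will be quoted.

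**The effect is small.** At 10% missing, a 20% rate loses 2 points, about half its standard error (√(0.20 × 0.80/92) = 4.2 points). The study is descriptive, tests no hypothesis, and no decision rule uses these percentages. This also stands. But the error is systematic and downward relative to the rate among assessed patients, and its direction is known in advance.

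**Skin and adhesion rest on inference.** The SAP 8.1 entry sits in a table of decimal places, so it is weak evidence for a denominator rule. That is fair: for Table 14.3.8 the denominator is implied, not stated. No other rule is given.

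**Stronger readings that the documents do not support.**

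- A reader might infer that missing patients are counted as normal. They are in no category, Normal is diluted by the same factor, and the ratio of Normal to Abnormal is unchanged.
- A reader might infer that the UTI objective is understated by this rule. That objective is reported in Table 14.3.9, a cumulative proportion over 16 weeks and not a by-visit table.
- A reader might infer that an assessed-only denominator recovers the true rate when patients leave because of a skin reaction. It does not, because those patients are then absent from numerator and denominator alike. Reactions recorded as adverse events are still captured in the adverse event tables.

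Protocol 4.6.10 asks patients who stop treatment to return for an early-discontinuation assessment, which could raise A. The SAP does not say whether that assessment counts as Visit 2 or EOS, so its effect cannot be judged.

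**Conclusion.** The point holds. Following the stated footnotes, every by-visit category percentage in Tables 14.3.11, 14.3.13 and 14.3.14 is multiplied by assessed/N and the categories fail to sum to 100% whenever assessments are missing. Table 14.3.8 most plausibly follows the same rule.

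At the plan's own 10% drop-out the factor is 0.90, a relative understatement of about 10%. This takes the planned drop-out as the fraction missing at the visit and N as 102; the actual missingness is unknown. The understatement is measured against the rate among assessed patients, not against an unknown true rate in all treated patients.

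The primary adverse event analysis is not affected. The correction should be made, but it does not threaten the study's main conclusion.

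**What to change.** In SAP 8.1 and the footnotes of Tables 14.3.8, 14.3.11, 14.3.13 and 14.3.14, state that the denominator of a by-visit percentage is the number of safety-set patients with a non-missing assessment of that parameter at that visit. Print that number for each visit, and add a Not assessed row. Keep the full safety set as denominator for the adverse event incidence tables.

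The cost is footnote wording, one displayed n and one row per table or parameter. No new data are needed. The downside is that denominators vary by visit, which the displayed n makes plain. The change removes the arithmetic dilution and makes missingness visible. It does not remove bias from informative drop-out, and the report should say so when it interprets EOS rates.
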